12.3 Clinical Laboratory Tests

Selected hematology and serum chemistry parameters including Alanine Aminotransferase (ALT), Aspartate Aminotransferase (AST), Creatinine, Total Bilirubin, Hemoglobin, Neutrophiles and Platelets Count will be summarized for Safety population. All other laboratory results, including pregnancy test results, will be listed only.

For all quantitative parameters, the actual value and the change from baseline by scheduled time of evaluation will be summarized by dose levels and dose schedule for each study visit using descriptive statistics. Both scheduled and unscheduled visits will be considered for baseline derivation.

Laboratory parameters are also graded according to CTCAE v5.0 for the selected parameters listed above. A shift table, presenting the 2-way frequency tabulation for baseline and the worst post-treatment value according to the NCI-CTCAE grade, will be provided. Laboratory parameters with CTCAE grading in both high and low directions will be summarized separately. Both scheduled and unscheduled post-treatment visits will be considered in tabulation of the worst post-treatment value. Additionally, the number and percentage of participants with the following potentially clinically significant abnormal liver function test will be presented:

- ALT >3xULN, \geq 5xULN, \geq 10xULN, and \geq 20xULN
- AST >3xULN, \geq 5xULN, \geq 10xULN, and \geq 20xULN
- Total bilirubin >2xULN

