7.3 Analysis Visit Window

Data will be analyzed by scheduled visits, where appropriate. Data that are collected from an unscheduled visit will not be included in the by-visit summary tables but will be presented in the listings. However, data collected at unscheduled visits will also be considered for toxicity grading for laboratory assessments. Both unscheduled and out-of-window imaging assessments will be included in efficacy analysis.

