8.8 Prior and Concomitant Medications and Procedures

Prior and concomitant medications and procedures will be coded using the latest World Health Organization Drug (WHODrug) Dictionary version available. Unless specified otherwise, summaries of prior and concomitant medications will be presented by Anatomical Therapeutic Class (ATC) Level 2 and PT with numbers and percentages for subjects in the Safety Population.

A subject who takes more than one medication will be counted only once if these medications belong to the same ATC Level 2 classification.

In the summary tables, prior medications and concomitant medications and procedures will be presented by decreasing frequency of subjects overall within each ATC Level 2 class and then similarly by decreasing frequency of subjects overall within each preferred term. In cases of ATC Level 2 classes or preferred terms with equal frequencies, medications will be sorted alphabetically.

Prior medications/procedures are defined as those medications/procedures that started prior to the first administration of the study drug. Concomitant medications/procedures are defined as those medications/procedures taken on or after the first administration of the study drug till 30 days after the last dose of study treatment, or the start of subsequent anticancer therapy, whichever occurs first.

A prior medication/procedure could also be classified as "both prior and concomitant medication/procedure" if the end date is on or after first dose of study treatment. In the listing, it will be indicated whether a medication is prior-only, concomitant-only, or both prior and concomitant medication.

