12.2 Adverse Events

All reported AEs will be coded using the MedDRA with the most current version for the purposes of summarization. NCI CTCAE Version 5.0 will be used for grading AEs. AEs will be collected and recorded for each patient from the day of signing the ICF until 30 days after last trial intervention administration or until participant started alternative anticancer

therapy, whichever is sooner. Prior to receiving trial intervention, only AEs considered related to trial procedures, and all serious adverse events (SAEs) will be summarize by study phase and treatment arms.

A treatment-emergent adverse event (TEAE) will be defined as any event that was not present prior to the initiation of trial intervention(s) or any event that worsens in either intensity or frequency following exposure to trial intervention(s) through 30 days after cessation of trial treatment or until the participant starts alternate anti-cancer therapy, whichever is sooner, with exception of treatment related SAEs which were reported until the end of survival follow-up and will be included as TEAE regardless of time of onset.

All TEAEs reports will summarize by dose levels and dose schedules unless otherwise specified.

Overall TEAE summaries will be presented for the Safety Population. The summaries will include the following categories:

- All TEAEs
- TEAE by CTCAE grade
- TEAEs with CTCAE Grade ≥ 3
- TEAE leading to study treatment discontinuation
- TEAE leading to death
- TEAE related to study treatment
 - TEAEs related to study treatment are defined as 'definitely related', 'probably related', or 'possibly related', to study drug as assessed by the Investigator.
- TEAE related to study treatment with CTCAE Grade ≥ 3
- TEAE related to study treatment leading to treatment discontinuation
- TEAE related to study treatment leading to study treatment interruption
- TEAE related to study treatment leading to study treatment reduction
- TEAE related to study treatment leading to death
- Serious TEAE
- Serious TEAE leading to treatment discontinuation
- Serious TEAE leading to death
- Serious TEAE related to study treatment
- Serious TEAE related to study treatment leading to study treatment discontinuation
- Serious TEAE related to study treatment leading to death

Any missing onset date, causality, or severity must be queried for resolution. Unresolved missing causality will be handled according to the following rules:

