12-lead ECG ^m		X	X				X				X		X		X			X				
Pregnancy test ⁿ		X	X								X				X			X		X	X	
Clinical safety lab tests ^o		X	X								X				X			X		X	X	
CBC with diff. (included in safety lab tests)													X	X		X	X		X ^h			
ctDNA whole blood ^p		X	X								X		X			X		X ^h	X ^h	X		
Tumor biopsy ^{q,r,s}		X^q														X ^r				X ^s		

				Cycle 0																									
	Dwa						Food I			r	PK Cycle ^b								Additional		EOT/	Safety	Survival						
	Pre- screening	Screening ^a	Ef For	fect mul l (P		on	Effe Form	Fasted (Food Effect) or Formulation 2 (PK Bridging)			Effect) or brmulation 2			Fasted	Fasted			Cycle 1				Cycle 2				tional cles	ET ^c	Follow -up Visit ^d	Follow- up ^e
Trial Days Procedures/ Assessments ^f	-180 to -1	-28 to -1	1 ^a	2	3	4	5 (+5)	6	7	8	1ª	1	8 (+2		15 (+2)	1 (+3)	8 (+2)	15 (+2)	1 (+3) ^g	8 (+2) ^h	Within +7 days of Disc of Trt date	30 days after last dose (+14 days)	Every 90 days (±14 days)						
Central testing for molecular eligibility ^t	X																												
Archival tumor tissue ^u	X ^t	X																											
RP-1664 dispensed/coll ected				Dispensed and collected according to Pharmacy Manual																									
RP-1664 administration			X See Section Error! Reference source not found., Dosing and Administration																										
Review of dosing diary ^w												X	X		X	X	X	X	X		X								
PK sample collection ^x			X	X	X	X	X ^y	Х	X	X	X ^z	X	Xz	:		X ^z	Xz		Xz										

			PK	Cvcl	e Foi	Cycl		ct o	r	PK											
	Pre-			PK I	Bridg	ging Col				Cycle ^b	_						Addi	tional	EOT/	Safety Follow	Survival
	screening	Screening ^a	Ef For	d (Fo fect) mula 1 (PK idgin	or tion	Faste Eff Form (PK l	ect) ulat	or tion	2	Fasted		Cycl	e I		Cycle 2		Cy	cles	ET°	-up Visit ^d	Follow- up ^e
Trial Days	-180 to -1	-28 to -1	1 ^a	2	3 4	5 (+5)	6	7	8	1 ^a	1	8 (+2)	15 (+2)	1 (+3)	8 (+2)	15 (+2)	1 (+3) ^g	8 (+2) ^h	Within +7 days of Disc of Trt	30 days after last dose	Every 90 days (±14 days)
Procedures/ Assessments ^f																			date	(+14 days)	
Blood collection (4β- OHC/total cholesterol) ^{aa}		X	X										X		X			X			
Urine collection ^{bb}						X															
Tumor assessments: RECIST or INRC ^{cc}		X^{dd}									Т			tumor a		nts. Ther	om Cycle eafter, e				
Serum tumor markers ^{ee}		X	7	To be	asses	sed at l	east	onc	е ре	er cycle fro	cycle from Cycle 0 Day 1 and at EOT (or as per standard of care schedule).										

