AE assessment				To	be c	collected	l fro	m th	he ti	me of ICF	sig	ning; se	e Section	Error!	Refere	nce sour	ce not fo	ound.			

[figure not shown]
						Cycl	e 0														
	_					r Food I ging Col			r	PK Cycle ^b									EOT/	Safety	Survival
	Pre- screening	Screeninga	Ef Form	d (Fo fect) mula l (PK idgin	or tion	Fasto Eff Form (PK I	ect) ulat	or tion	2	Fasted		Cycle	e 1		Cycle 2			tional cles	EOT/ ET°	Follow -up Visit ^d	Follow- up ^e
Trial Days	-180 to -1	-28 to -1	1ª	2	3 4	5 (+5)	6	7	8	1ª	1	8 (+2)	15 (+2)	1 (+3)	8 (+2)	15 (+2)	1 (+3) ^g	8 (+2) ^h	Within +7 days of Disc of Trt	30 days after last dose	Every 90 days (±14 days)
Procedures/ Assessments ^f																			date	(+14 days)	
Concomitant medications/ procedures (transf. and growth factors included)						To be co	lleci	ted f	ron	n the time (of So	creening	Visit th	rough th	e Safety	Follow-	up visit				
Post-trial therapy data collection ^{ff}																					X
Survival status																					X

- a. **Screening:** Screening Period extends from Day -28 to Day -1. Screening assessments may be used as Cycle 0 Day 1 assessments if performed within 96 hours of the first dose of RP-1664 except for the ctDNA blood draw, vital signs, and ECGs. ECOG or Lansky performance status and PE that are completed within 24 hours of first dose of RP-1664 may be used a Cycle 0 Day 1 assessments. Participants must continue to meet eligibility criteria prior to first dose of RP-1664 on Cycle 0 Day 1.
- b. Cycle 0: The 2-day PK Cycle 0 is not required for participants in the food effect or PK bridging portion of the trial.
- c. **EOT/ET:** A post-treatment/ET visit will be conducted following the last dose of trial intervention and within 7 days after the date of treatment discontinuation but prior to the start of the next anticancer therapy.
- d. Safety Follow-Up: Required for all participants who discontinued from the trial for whatever reason.
- e. **Survival Follow-Up:** Survival follow-up will be conducted approximately every 90 days (±14 days) after date of treatment discontinuation until the end of trial (for up to 6 months), participant withdrawal of consent to trial, or death. This follow-up may be conducted by telephone contact or standard method used by participating centers and agreed by the Sponsor.

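### The worst-grade laboratory and liver-threshold tables do not stop at the start of new anticancer therapy, so toxicity of the next treatment could be counted against RP-1664

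*SAP*

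**What the plan says.** SAP 12.3 cross-tabulates the baseline CTCAE grade against the worst later grade for ALT, AST, creatinine, bilirubin, hemoglobin, neutrophils and platelets. The period is set by one sentence: "Both scheduled and unscheduled post-treatment visits will be considered in tabulation of the worst post-treatment value". The section then adds that "the number and percentage of participants with the following potentially clinically significant abnormal liver function test will be presented", with no time limit stated. SAP 7.3 supplies none; it says only that "data collected at unscheduled visits will also be considered for toxicity grading for laboratory assessments".

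Two other sections do set a limit. SAP 12.2 counts TEAEs "through 30 days after cessation of trial treatment or until the participant starts alternate anti-cancer therapy, whichever is sooner", except that treatment-related SAEs count whenever they begin. SAP 8.8 takes concomitant medications "till 30 days after the last dose of study treatment, or the start of subsequent anticancer therapy, whichever occurs first".

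In the schedules (SAP 14.1.1), clinical safety laboratory tests are marked at both the end-of-treatment (EOT) visit and the Safety Follow-up visit. Footnote c places EOT "within 7 days after the date of treatment discontinuation but prior to the start of the next anticancer therapy". Footnote d says of Safety Follow-up only that it is "Required for all participants who discontinued from the trial for whatever reason"; it sets no order relative to the next therapy.

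**The concern.** These participants have advanced disease, and many will stop RP-1664 because of progression. Some may start another treatment in the weeks between EOT and Safety Follow-up. If that treatment lowers blood counts or raises liver tests, the Safety Follow-up sample records it, and SAP 12.3 as written enters it as the worst grade on RP-1664.

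The parameters tabulated are the ones most exposed to this. The protocol synopsis names neutropenia as the anticipated toxicity of RP-1664, and a cytotoxic next-line regimen could give the same signal. AE collection also ends at new therapy (SAP 12.2), so a high grade in the shift table would usually have no TEAE and no causality assessment beside it. The exception is an SAE judged related to RP-1664. Two safety displays for the same participant could then disagree, and the report would have no pre-specified way to say which reflects the drug.

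**Working it through.** The plan states no figure on this point, so the check compares the rules and then gives an illustration of scale.

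**1. Analysis windows side by side**

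| Display | End of window | Stops at new therapy? |
|---|---|---|
| TEAEs (SAP 12.2) | 30 days after treatment | Yes, related SAEs excepted |
| Concomitant medications (SAP 8.8) | 30 days after last dose | Yes |
| Worst laboratory grade (SAP 12.3) | None stated | No |
| Liver-threshold counts (SAP 12.3) | None stated | No |
| Laboratory grading in general (SAP 7.3) | None stated | No |

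**2. Can a sample follow new therapy?** Table 1 times the Safety Follow-up visit as "30 days after last dose (+14 days"), that is Day 30 to 44. SAP 4.2 and Table 9 allow 14 days either side: 30 − 14 = Day 16 to 30 + 14 = Day 44. Take a participant with EOT on Day 5, chemotherapy from Day 10, and Grade 4 neutropenia at a Day 30 Safety Follow-up visit. The schedule permits this under either window. If the earlier worst grade was 2, the shift table shows Grade 4, while an onset after Day 10 falls outside the TEAE window.

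**3. When does it change a table?** Three things must all happen: new therapy starts before the sample, the new therapy causes an abnormality, and the resulting grade exceeds that participant's earlier worst grade. If it only equals the earlier grade, nothing changes.

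**4. Illustration on assumed inputs.** Let s be the share who start new therapy before the sample, and q the chance that it then produces a grade worse than the earlier worst. Neither is in the documents. Assume s = 10% to 50% and q = 10% to 30%, so s × q = 0.01 to 0.15. The expected number affected is n × s × q, and the chance of at least one is 1 − (1 − s × q)^n.

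| n | Expected number | Chance of at least one |
|---|---|---|
| 3 (minimum cohort from Dose Level S) | 0.03 to 0.45 | 3% to 39% |
| 20 (one expansion cohort) | 0.2 to 3.0 | 18% to 96% |
| 80 (whole trial) | 0.8 to 12 | 55% to over 99% |

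One affected participant moves a rate by 1/3 = 33 percentage points in a cohort of 3, and by 1/20 = 5 points in a cohort of 20. With a stop at new therapy the number is 0.

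**5. What would a 30-day limit do?** Under Table 1 the visit may fall on any of 44 − 30 + 1 = 15 days, and 14 of them lie beyond Day 30. Under the wider window it is 14 of 44 − 16 + 1 = 29 days. These values would be lost whether or not new therapy had started.

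**The case against.** The strongest case on the other side is that little depends on these tables. The TEAE endpoint has its own cut-off. DLTs end with Cycle 1. Dose decisions rest on DLT-evaluable participants and committee review, and SAP 7 calls the analysis purely descriptive. All of this stands. A reader might infer that dose or schedule selection would be distorted, but no section bases such a decision on the final shift table.

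The size is also unknown. Inclusion criterion 7 largely enrols people who have exhausted, cannot take or decline standard options, so few may start something new within weeks. RP-1664 is itself expected to cause neutropenia, which makes it harder for a later value to exceed the earlier worst. This stands too, and is why the figures above are only an illustration.

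Nor is the problem hidden. Later-therapy dates are recorded and listings are sorted by date, so affected values could be found. But finding them after the tables are produced means deciding afterwards which high grades to set aside.

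A reader might also infer that the laboratory tables should simply take the whole TEAE window. The documents do not support that. The 30-day part would remove most Safety Follow-up laboratory values under Table 1, including late RP-1664 cytopenias in participants on no other drug. It could also drop the laboratory value behind a related SAE that SAP 12.2 still counts as a TEAE.

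Finally, only the synopsis of the protocol is available, so a rule elsewhere on the timing of the Safety Follow-up visit cannot be excluded. None appears in the text at hand.

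**Conclusion.** The gap is real and limited. As written, SAP 12.3 can attribute another drug's laboratory toxicity to RP-1664, and nothing in the available text prevents it. The effect is confined to descriptive tables: the shift tables by worst grade and the liver-threshold counts.

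The documents support saying that such toxicity could be counted, not that it will be. The range of 0.8 to 12 of 80 participants rests wholly on the assumed s and q and should not be read as an estimate. The inconsistency with SAP 12.2 and 8.8 does not depend on those inputs, nor on which Safety Follow-up window is correct. It should be settled before database lock.

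**What to change.** Add one sentence to SAP 12.3: values taken on or after the start date of alternate anticancer therapy are excluded from the shift tables, the worst-grade tabulation and the liver-threshold counts, and are listed with a flag. Do not add a limit at last dose + 30 days, so that Safety Follow-up values from participants on no new therapy stay in the tables.

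The dates are already collected (SAP 14.1.1, Table 1, footnote ff), and SAP 7.8 gives the rule for partial ones. That rule can place a start date too early or too late, so the listing should mark imputed dates.

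The cost is small: no new data, and some values taken after the switch move from tables to listings. Separately, reconcile the Safety Follow-up window, which is 14 days either side in SAP 4.2 and Table 9 but only 14 days after in Table 1.

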12.4 Vital Signs

The observed value and changes from baseline of blood pressure, heart rate, and temperature will be summarized and listed by visit for Safety Population.

12.5 12-lead ECG

Descriptive statistics of actual value and change from baseline value for ECG parameters, including heart rate, PR interval, QRS duration, QT interval, and QTcF interval (Fridericia's corrections) will be presented for baseline visit and scheduled

post-treatment visit. The average of triplicate 12-lead ECG results at each timpoint will be used for descriptive statistics. Standard and triplicate 12-lead ECG data will be listed for each participant and time point for Safety population.

Overall ECG interpretation category (normal, abnormal NCS [not clinically significant], abnormal CS [clinically significant], and not evaluable) is collected in the CRF at baseline and each scheduled post-baseline visit. Shifts tables (shift from baseline to the worst post-baseline values) will be presented.

The QTcF will be categorized into the following categories to identify potentially clinically important changes:

- QTc interval >450 msec and ≤480 msec
- QTc interval >480 msec and \leq 500 msec
- OTc interval >500 msec

The change from baseline in QTcF will also be categorized separately as follows:

- QTc interval increases from baseline by >30 msec and ≤ 60 msec
- QTc interval increases from baseline by >60 msec

For the number of subjects meeting each category for the post-baseline results, the numerator is the number of subjects with meeting the criterion at post-baseline and the denominator is the number of subjects with normal baseline and at least one post baseline assessment in the Safety Population. For the number of subjects meeting each category for the change from baseline, the numerator is the number of subjects with meeting the criterion at post-baseline and the denominator is the number of subjects with baseline and at least one post baseline assessment in the Safety Population.

Box plots for absolute and change from baseline for QTcF will be produced based on the Safety Population and the number of patients with data at the relevant timepoints. Timepoints where there are <3 observations at a treatment group will not be presented. All ECG tables and listings will be reported on the safety population.

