- e. Significant ventricular or supraventricular arrhythmias, including history of Torsades de pointes (TdP) unless all risk factors that contributed to TdP have been corrected. Participants with chronic rate-controlled atrial fibrillation in the absence of other cardiac abnormalities are eligible.
- f. Family history of sudden unexplained death or long electrocardiogram (ECG) interval measured from the onset of the QRS complex to the end of the T wave (QT syndrome)
- 7. Mean resting QT interval corrected for heart rate (QTc) interval using the Fridericia formula (QTcF) > 470 msec (as calculated per institutional standards) demonstrated by at least 2 ECGs ≥ 1 minute apart at trial entry.
- 8. Moderate or severe hepatic impairment (i.e., Child-Pugh class B or C).
- 9. Uncontrolled hypertension (systolic blood pressure [BP] ≥ 160 mmHg and/or diastolic BP ≥ 100 mmHg) despite adequate treatment prior to first dose of treatment.
- 10. Persistent Grade > 1 non-hematological toxicity from prior cancer therapy (except alopecia, anorexia or toxicity that is stable and poses no significant risk to the participant). Grade 2 peripheral neuropathy after documented treatment with taxanes and/or platinum-based therapy is allowed.
- 11. Chemotherapy, small molecule or biologic antineoplastic agent given within 21 days or < 5 half-lives, whichever is shorter, prior to first dose of trial intervention. For compounds for which 5 half-lives is ≤ 21 days, a minimum of 10 days between termination of the prior treatment and administration of trial intervention is required.
- 12. Other anticancer therapy (chemotherapy, immunotherapy, hormonal anticancer therapy, biological therapy, lanreotide/octreotide for neuroendocrine tumors (NETs)/neuroendocrine carcinomas (NECs), or other novel agent) while the participant is receiving trial intervention. For participants with breast or prostate cancer, continuation of long-term luteinizing hormone-releasing hormone (LHRH) or gonadotrophin releasing hormone (GnRH) are allowed if these medications were prescribed for at least 4 months before trial entry.
- 13. Previously prescribed receptor activator of nuclear factor kappa B ligand (RANKL) inhibitor initiated less than 4 months prior to trial entry. Bisphosphonates are allowed if initiated/administered at least 28 days prior to enrollment.
- 14. I-131 Meta-Iodo-Benzyl-Guanidine (MIGB) therapy within 6 weeks prior to initiation of trial treatment.

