7. DEFINITIONS AND CONVENTIONS FOR DATA HANDLING

All analyses will be performed using SAS® Version 9.4 or higher.

Unless specified otherwise, the analyses of data collected will be descriptive and summaries will be presented separately for each dose level, dose schedule and in total for the specified analysis population. Statistical analysis will be purely descriptive and no formal hypothesis testing or comparative analysis between dose level and dose schedule will be performed. Confidence intervals (CIs) will be constructed at two-side 95% level where appropriate.

Frequency distributions for categorical variables will be provided as the number of subjects in the category and the percentages of the total number of subjects in the given population as noted. Percentages will be reported to one decimal place.

The descriptive statistics for continuous variables will be the number of subjects, mean, standard deviation, median, lower and upper quartile, minimum and maximum. Mean and median will be reported to 1 decimal place, while the standard deviation will be reported to 2 decimal places. Minimum and maximum will be reported the same as the original data.

Summary tables may be replaced with listings when appropriate. For instance, an AE Frequency table may be replaced with a listing if it only contains a few unique preferred terms (PTs) reported on relatively few subjects.

Shift tables will be utilized to summarize clinical laboratory tests and neurological exams when applicable.

All tables will be summarized by study cohorts, treatment, dose level and dose schedule and include an overall column unless otherwise specified.

All listings will be sorted by study cohorts, dose level and dose schedule, subject ID and, if applicable, by visit date unless otherwise specified in the text.

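### SAP 12.5 divides all subjects meeting an absolute QTcF category by normal-baseline subjects only, and gives no QTcF cut-off for 'normal', so as written the percentage is not a proportion

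*SAP*

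**What the plan says.** SAP 12.5 (12-lead ECG) sorts QTcF into three absolute categories, of which the lowest is "QTc interval >450 msec and ≤480 msec"; the others are >480 to 500 msec and >500 msec. For these it sets the percentage as follows: "the numerator is the number of subjects with meeting the criterion at post-baseline and the denominator is the number of subjects with normal baseline". The denominator further requires a post-baseline assessment and is taken within the Safety Population.

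The next sentence, for the change-from-baseline categories, uses the same numerator wording, but there "the denominator is the number of subjects with baseline and at least one post baseline assessment in the Safety Population". That rule has no normal-baseline condition.

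No QTcF value is attached to 'normal baseline'. SAP 7.1 defines only the timing of baseline. The only other 'normal' in 12.5 is a different variable: "Overall ECG interpretation category (normal, abnormal NCS [not clinically significant], abnormal CS [clinically significant], and not evaluable) is collected in the CRF".

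Protocol exclusion criterion 7 removes participants whose mean resting QTc is above a limit "using the Fridericia formula (QTcF) > 470 msec". Entry at 451-470 msec is therefore permitted.

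SAP 7 expresses categorical results as "percentages of the total number of subjects in the given population as noted", and says that "summaries will be presented separately for each dose level, dose schedule and in total".

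**The concern.** A percentage is a proportion only if everyone counted in the numerator is also in the denominator. Here the baseline condition is applied to one side. A participant who enters at 460 msec and stays there meets the lowest category after baseline. If 'normal' means 450 msec or less, that participant is excluded from the denominator.

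The undefined term adds a second problem. 'Normal' could mean QTcF of 450 msec or less, or it could mean a normal overall ECG interpretation, which can be abnormal for reasons unrelated to QT. The two readings give different denominators.

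At stake is the accuracy of the QTcF safety tables by dose level and schedule. Safety and tolerability is a primary objective, and SAP 13 has data reviewed descriptively after each dose cohort to inform dose selection.

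**Working it through.** The plan gives no figure to reproduce here, so the check is of the wording, followed by arithmetic on assumed inputs.

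**Inputs from the documents.** The numerator and denominator rules and the category limits (SAP 12.5); the 470 msec entry limit (protocol exclusion 7); about 80 participants exposed (SAP 4.3); cohorts of at least 3 from Dose Level S (SAP 4.1).

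**Assumed inputs.** All 80 have a baseline and a post-baseline ECG; 'normal' means ≤450 msec; the share with a non-normal baseline; and the numbers entering or staying in a category.

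**Formulas.** Let N be all subjects, Nn those with normal baseline, p = 1 − Nn/N, a the normal-baseline subjects in the category and b the non-normal-baseline subjects in the category.

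- Literal rule: (a + b)/Nn
- All subjects: (a + b)/N
- Emergent (new entrants only): a/Nn
- Literal minus emergent = b/Nn, which is zero if b = 0
- Literal divided by all-subject = N/Nn = 1/(1 − p): 1.05, 1.11 and 1.25 at p = 5%, 10% and 20%

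**Category >450 to 480 msec, N = 80:**

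| p | Nn | a | b | Literal | All subjects | Emergent |
|---|---|---|---|---|---|---|
| 5% | 76 | 8 | 0 / 2 / 4 | 10.5 / 13.2 / 15.8% | 10.0 / 12.5 / 15.0% | 10.5% |
| 10% | 72 | 7 | 0 / 4 / 8 | 9.7 / 15.3 / 20.8% | 8.8 / 13.8 / 18.8% | 9.7% |
| 20% | 64 | 6 | 0 / 8 / 16 | 9.4 / 21.9 / 34.4% | 7.5 / 17.5 / 27.5% | 9.4% |

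When b > 0, the literal figure is above both consistent figures.

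**Above 480 msec, p = 10%.** Suppose 2 of the 8 non-normal and 1 of the 72 normal-baseline subjects exceed 480 msec. The literal rule gives 3/72 = 4.2%; restricting the numerator to normal baselines gives 1/72 = 1.4%; all subjects gives 3/80 = 3.8%. Restricting the numerator produces a proportion, but it leaves out two of the three subjects.

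**If 'normal' means overall ECG interpretation.** With 15 subjects in the category and 20%, 30% or 50% not normal, the table prints 15/64 = 23.4%, 15/56 = 26.8% or 15/40 = 37.5%, against 15/80 = 18.8%.

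**Values above 100%.** In a column of 3 with one non-normal-baseline subject who stays in the category and two new entrants, the rule prints 3/2 = 150%. To see how often this could happen, take the number of non-normal baselines as binomial(n, p), new entrants as binomial(Nn, 10%) and b as binomial(n − Nn, persistence), and find P(a + b > Nn). This includes columns with a zero denominator and at least one subject in the category. With p = 10% and persistence of 50% to 100%, it is 1.0% to 3.0% for columns of 3 and 0.1% to 0.6% for columns of 6. As a check, for n = 3 with 100% persistence: 0.243 × 0.01 + 0.027 + 0.001 = 0.030.

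**The case against.** The best defence is that SAP 7 makes a percentage refer to a noted population, and SAP 12.5 notes one: subjects with normal baseline and a post-baseline assessment. An ordinary reader would count only members of that population, and the result would be a legitimate treatment-emergent proportion. Since the lowest category starts above 450 msec, ≤450 msec is also the natural meaning of 'normal'; the overall interpretation sits in its own paragraph with its own output.

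That reading is possible, but the SAP does not state it and still gives no msec value. It would also remove participants entering at 451-470 msec from the >480 and >500 msec rows. Other outputs recover some of this. A rise from 470 msec or less to above 500 msec exceeds 30 msec, so it appears in a change-from-baseline row. Cover for >480 to 500 msec is only partial: a rise from 470 to 485 msec is 15 msec and appears in neither set of rows. QTcF descriptive statistics, box plots and listings also remain.

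Several points on the other side stand. The magnitudes are hypothetical and modest when few baselines are non-normal. Values above 100% need very small columns, where readers look at counts and listings anyway. The overall-interpretation figures rest on the less natural reading. A QTcF shift table is useful but is not needed to cure the defect.

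**Conclusion.** The concern holds. As written, the rule gives a ratio whose numerator is not contained in its denominator, and the 470 msec entry limit makes that a practical possibility. Under the ≤450 msec reading, the printed figure exceeds the all-subject rate by a factor of 1/(1 − p), provided the category is not empty. It exceeds the emergent rate only if someone with a non-normal baseline meets the category. In the 10% example the excess over the all-subject rate is 1 to 2 percentage points and the excess over the emergent rate is 0 to 11 points. These sizes rest wholly on assumed baseline and post-baseline counts.

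The consequence is confined to descriptive safety summaries. DLTs are judged participant by participant under SAP 12.1, and no test or sample size depends on these percentages. The rule should be corrected before the tables are programmed, but it does not threaten the trial's main conclusions.

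**What to change.** Use the same subjects above and below the line. Report each absolute category by worst post-baseline QTcF, over all Safety Population subjects with a baseline and at least one post-baseline QTcF.

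If a treatment-emergent rate is also wanted, define it for each category: subjects whose baseline was below that category and who then reach it, over all subjects whose baseline was below that category. In the 10% example this gives 7/72 for >450 to 480 msec and keeps those who entered at 451-470 msec in the >480 and >500 msec rows.

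Replace 'normal' with baseline categories in msec. A shift table of baseline QTcF category by worst post-baseline category would be a helpful option. The shift tables already in 12.5 appear, from their position, to concern overall interpretation. The change-from-baseline rule needs no change.

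The cost is one or two SAP sentences and minor table programming, with no new data.
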